7.2 PARTICIPANT DISCONTINUATION/WITHDRAWAL FROM THE STUDY

Participants are free to withdraw from participation in the study at any time upon request.

An investigator will discontinue or withdraw a participant from the study for the following reasons:

- Pregnancy or breastfeeding
- Significant study intervention non-compliance
- Any clinical adverse event (AE), laboratory abnormality, or other medical condition or situation which occurs such that continued participation in the study would not be in the best interest of the participant (including malignancy)
- New or recurrent Centers for Disease Control and Prevention (CDC) category C AIDS-indicator condition.
- If the participant meets an exclusion criterion (either newly developed or not previously recognized) that precludes further study participation
- Participant unable to receive CD24Fc for 2 doses

- Development of life-threatening infection or clinical reason deemed to be life-threatening by the physician
- Request of the primary care provider or Investigator if s/he thinks the study is no longer in the best interest of the subject.
- If the subject is judged by the Investigator to be at significant risk
- The following laboratory abnormalities
 - HIV RNA>200 copies/mL (2 readings at least 2 weeks apart)
 - o Decrease in eGFR to <30mL/min, confirmed by immediate repeat testing
 - Elevation of ALT >5x OR AST >5x Day 0, confirmed by immediate repeat testing
 - Abnormal elevation of ALT >3 x Day 0 and total bilirubin >2 x ULN, confirmed by immediate repeat testing
 - For participants with entry CD4+ T cell count between 350 500 cells/mm³, confirmed absolute and percent CD4+ decline greater than 25% of baseline.
 - For participants with entry CD4+ T cell count between 501 to 800 cells/ mm³, a confirmed absolute and percent CD4+ T cell decline greater than 33% of baseline.
 - For participants with entry CD4+ T cell count greater than 800 cells/ mm³, a confirmed absolute and percent CD4+ T cell decline greater than 50% of baseline.
 - Occurrence of Grade 4 anemia/neutropenia or recurrence of Grade 3 anemia/neutropenia.

The reason for participant discontinuation or withdrawal from the study will be recorded in the study record. Subjects who sign the informed consent form and are randomized but do not receive the study intervention may be replaced. Subjects who sign the informed consent form, and are randomized and receive the study intervention, and subsequently withdraw, or are withdrawn or discontinued from the study, will not be replaced.

Participants who prematurely discontinue the study agent due to toxicity will be followed closely for resolution of symptoms, until final outcome is known or until the end of the study follow-up period.

Subjects who discontinue the agent due to toxicity, as well as those who elect to discontinue study drugs prior to treatment completion for medical or personal reasons, will continue to follow the general study schedule of assessments unless unwilling to do so. The participant should have an end of treatment visit scheduled as soon as possible after all therapy is discontinued, if he/she is willing. Any subject continuing in the study will be followed closely for resolution of active laboratory abnormalities or adverse events that are considered related to the study agents.

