7 STUDY INTERVENTION DISCONTINUATION AND PARTICIPANT DISCONTINUATION/WITHDRAWAL

7.1 DISCONTINUATION OF STUDY INTERVENTION

If a clinically significant finding is identified (including, but not limited to changes from baseline) after enrollment, the investigator or qualified designee will determine if any change in participant management is needed. Any new clinically relevant finding will be reported as an adverse event (AE).

AEs are evaluated according to the Division of AIDS (DAIDS) Table for Grading the Severity of Adult and Pediatric Adverse Events, version 2.1, July 2017. All adverse events will be reviewed by the Principal Investigator (PI) and the study team at team meetings. All Grade 3 events will be evaluated by the PI and the designated Medical Monitor. Grade 4 and Grade 5 events will be reported to the Sponsor and the Medical Monitor within 24 hours of notification of the event.

CD24Fc infusion will be paused for a single subject for any grade 4 event pending review by the Medical Monitor. The MM will include review of this event in a report issued to the DSMB every 12 weeks. Administration of medication will be paused for all subjects if 2 or more subjects have the same grade 4 adverse event deemed related to study drug. The MM will report these events to the DSMB and enrollment and dosing will be held for all pending review by the DSMB.

The study may be terminated after consultation with the Medical Monitor, DSMB and Sponsor, in the event that one or more of the following adverse reactions are not remediated within 2-4 hours, and in the opinion of the PI and Medical Monitor, are clinically relevant and constitute a substantial risk to the participants: cytokine release syndrome, hypotension, shortness of breath, disseminated intravascular coagulation, mental status changes.

Other criteria for study termination may include:

- the decision of the Medical Monitor or DSMB to stop further study visits
- the recommendation or decision for any reason of the PI that safety may be at risk or compromised by continuing the trial
- the decision of the Sponsor to terminate the study for any reason

The data to be collected at the time of study intervention discontinuation will include the following:

- Vital signs and physical examination
- Complete metabolic panel, complete blood count with differential, PT/INR
- Other laboratory tests that further evaluate a sign or symptom

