8.4.4 TIME PERIOD AND FREQUENCY FOR EVENT ASSESSMENT AND FOLLOW-UP

The occurrence of an adverse event (AE) or serious adverse event (SAE) may come to the attention of study personnel during study visits and interviews of a study participant presenting for medical care, or upon review by a study monitor.

All AEs including local and systemic reactions not meeting the criteria for SAEs will be captured in the study record. Information to be collected includes event description, time of onset, clinician's assessment of severity, relationship to study product (assessed only by those with the training and authority to make a diagnosis), and time of resolution/stabilization of the event. All AEs occurring while on study must be documented appropriately regardless of relationship. All AEs will be followed to adequate resolution. AEs and SAEs will be collected between Day 0 and Week 28 (completion of study).

Any medical condition that is present at the time that the participant is screened will be considered as baseline and not reported as an AE. However, if the study participant's condition deteriorates at any time during the study, it will be recorded as an AE.

Changes in the severity of an AE will be documented to allow an assessment of the duration of the event at each level of severity. AEs characterized as intermittent require documentation of onset and duration of each episode.

The PI or study coordinator will record all reportable events with start dates occurring any time after informed consent is obtained until the last day of study participation. At each study visit, the investigator will inquire about the occurrence of AE/SAEs since the last visit. Events will be followed for outcome information until resolution or stabilization.

All enrolled subjects who have received CD24Fc will be evaluated for safety with the laboratory assays done at each visit as outlined in section 8.2. Safety will be assessed by physical examination, vital signs, hematology, and chemistries. Vital signs will include pulse, blood pressure, respiratory rate, and oxygen saturation. The severity of signs, symptoms, and AEs will be determined by using DAIDS toxicity table, version 2.1. The CD24Fc infusion will be administered over a minimum of 1 hour. Subjects will be monitored after infusion is completed for 2 hours and repeat vital signs and laboratory results will be ascertained as needed based on reported symptoms.

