Enrollment and dosing will be paused for an individual subject who has a Grade 4 AE. After review by the Medical Monitor (MM) and reporting to the DSMB in the regularly scheduled report every 12 weeks, the MM will evaluate whether study participation for the subject should continue. During MM review, enrollment and dosing will not be paused for other study subjects.

If two subjects experience the same Grade 4 AE related to the study drug, all enrollment will be paused and all doses for enrolled subjects will be held. The MM will report to the DSMB within 24 hours and study dosing will halt until DSMB determination regarding continuation of study enrollment and dosing.

If one or more subjects experiences changes in mental status, DIC, dyspnea, cytokine release syndrome and/or hypotension related to the study drug, without remediation in 2-4 hours, the MM will report to the DSMB within 24 hours and the DSMB will review the report for possible study termination. During this review, enrollment and dosing will be halted for all subjects.

Safety and Efficacy Analyses

The primary safety endpoint will be assessed by Incidence and severity of any adverse events (AEs) during the administration of drug and 24 weeks after completion. Safety will be evaluated by assessment of clinical laboratory tests, physical examination at various time points during the study, and by the documentation for AEs. A statistical analysis plan (SAP) will be prepared and finalized prior to unblinding of subject's treatment assignment. This document will provide further details regarding the definition of analysis variables and analysis methodology to address all study objectives.

Safety and tolerability will be summarized by treatment arm, including Treatment Emergent Adverse events (TEAEs), and laboratory evaluations. No inferential analysis is planned for safety data. Adverse events will be coded using the most current version of the Medical Dictionary for Regulatory Activities

(MedDRA). TEAEs are defined as new or worsening AEs after the first dose of study medication, and will be summarized by system organ class, and preferred term. A list of subjects who have Severe Adverse Events (SAEs) and who discontinue from the study due to an adverse event will be provided.

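### Section 7.2 does not say whether its stopping criteria end study drug or observation, so a laboratory trigger after the last infusion can cut short safety follow-up and Week 28 data

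*Combined protocol and SAP*

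**What the plan says.** Section 7.2 opens its list with "An investigator will discontinue or withdraw a participant from the study for the following reasons". The list includes laboratory criteria (HIV RNA, eGFR, ALT/AST, ALT with bilirubin, CD4 decline, anaemia/neutropenia) and "Participant unable to receive CD24Fc for 2 doses". No item is limited to the dosing period. The general adverse-event item depends on the participant's best interest and is not in dispute here.

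Further on, the same section covers people who discontinue the agent because of toxicity and "those who elect to discontinue study drugs prior to treatment completion for medical or personal reasons". These participants "will continue to follow the general study schedule of assessments unless unwilling to do so". Dosed participants who leave, or who "are withdrawn or discontinued from the study, will not be replaced".

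Section 8.4.4 makes two statements about adverse events. One sets collection of AEs and SAEs from Day 0 to Week 28. The other has reportable events recorded if they start "any time after informed consent is obtained until the last day of study participation". Appendix A repeats both.

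NIH Addendum section 3 reproduces the withdrawal list, but says participation *could* be discontinued where section 7.2 says *will*. Its CD4 items lack the absolute-and-percent condition now in section 7.2.

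**The concern.** A criterion for stopping a drug and a criterion for ceasing to observe a person are different things, and section 7.2 does not keep them apart. Followed literally, the list removes from the study the participants whose laboratory results signal a possible safety or immune problem. The first primary endpoint (section 3.1.4) is adverse events during dosing and for 24 weeks afterwards, so these are the people whose later course matters most.

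The Week 28 secondary endpoints in section 3.1.5 are exposed in the same way: CD4, proviral DNA, troponin and elastography. CD4 is both a withdrawal trigger and an endpoint, so a confirmed fall at Week 16 could remove the largest declines from the Week 28 comparison. Elastography has no post-baseline measurement before Week 28 (section 1.3). Sections 9.4.1 and 9.4.2 name no method for missing values and leave the detail to a later SAP.

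**Working it through.** **1. The two rules side by side.**

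| Case | Withdrawal list (7.2) | Retention paragraph (7.2) | Result |
|---|---|---|---|
| Toxicity-driven trigger before the last infusion | Withdraw from study | Stay on schedule | Direct conflict; no order of precedence |
| Laboratory trigger at Week 6 or 16 | Withdraw from study | Not clearly covered: no agent left to discontinue | Only observation can end |
| Two doses missed, neither toxicity nor choice | Withdraw from study | Not covered | Observation ends |

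The second row can occur in practice: section 1.3 schedules chemistry, blood count, CD4 and HIV viral load at Weeks 6, 16 and 28.

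**2. Follow-up exposed per affected participant.** Inputs: last infusion at Week 4, last visit at Week 28 (section 1.3). Follow-up is 28 − 4 = 24 weeks.
- Trigger at Week 6: 28 − 6 = 22 weeks; 22/24 = 91.7%.
- Trigger at Week 16: 28 − 16 = 12 weeks; 12/24 = 50.0%.
- HIV RNA first raised at Week 6: the second reading comes at least 2 weeks later, so 28 − 8 = 20 weeks; 20/24 = 83.3%.

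These are upper limits at nominal visit times, because confirmation takes time.

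**3. How likely is the missed-dose route through a hold?** With ±4 days (section 8.1) the Week 2 dose can be given on Days 10–18 and the Week 4 dose on Days 24–32. To remove both, a hold must cover Day 10 to Day 32, which is 23 days inclusive. Section 7.1 provides that "CD24Fc infusion will be paused for a single subject for any grade 4 event pending review by the Medical Monitor", and Appendix A adds that "the MM will evaluate whether study participation for the subject should continue". But section 7.1 sends Grade 4 events to the Medical Monitor within 24 hours, and Appendix A requires a report to the DSMB within 24 hours when a trial-wide hold starts. A 23-day hold is possible but unlikely.

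**4. The Week 6 LDL.** A trigger found on Week 6 blood comes after the primary LDL sample. Earlier loss needs a trigger acted on before Week 6, two missed doses, or another listed reason such as pregnancy, non-compliance or a newly met exclusion criterion.

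The plan's sample size reproduces: n per arm = 2 × (1.960 + 0.842)² × (20/15)² = 27.9, so 28. The margin is 64 − 56 = 8 participants. No document gives a withdrawal rate to set against that 8, so a power figure would not measure this problem.

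**The case against.** The strongest reply is that adverse-event data are not lost. Section 8.4.4 and Appendix A fix collection of AEs and SAEs from Day 0 to Week 28, and sections 8.4.4, 8.4.6 and 8.4.7 keep known events and abnormal results under follow-up. This largely stands. A reader might infer that recording stops at withdrawal. The documents do not support that reading, because both statements are present and neither is said to govern withdrawn participants. What withdrawal clearly ends is the scheduled visits, where new events are asked about and endpoints measured.

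A reader might also infer that the primary LDL analysis is compromised. It is not shown to be: triggers after Week 6 cannot touch that sample, section 9.2 already allows 11% attrition, and no loss rate is given.

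A third tempting inference is that dosing holds will routinely force withdrawals. The 24-hour reporting steps make that remote, and a participant stopped for drug toxicity is already in the retained group.

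Nor are all the laboratory items confirmed findings: the anaemia/neutropenia item carries no confirmation requirement.

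Finally, the words discontinue *or* withdraw might be meant to include stopping drug alone. But the section heading and the sentence both refer to the study, and nothing elsewhere settles it.

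**Conclusion.** The concern holds as an unreconciled contradiction within section 7.2. Its firm core is the laboratory trigger met after Week 4, which under the text can end only observation. The direct conflict during dosing also stands. Two doses missed for other reasons are a genuine gap, but a hold is an unlikely way to reach it.

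The size is known per person (up to 22 or 12 of 24 follow-up weeks) and unknown for the trial, since no trigger or missed-dose rate is given. The likely loss is new-event ascertainment at visits and Week 28 secondary data, concentrated in participants with safety or immune signals. No bias figure and no power loss is claimed. The conclusion assumes that sites follow the list as written; a site that reads it as stopping drug only would lose little. The Addendum differences are housekeeping.

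**What to change.** Reconcile section 7.2, section 8.4.4 and NIH Addendum section 3 so that each listed reason states whether it ends study drug, observation or both. For dosed participants, separate the two. The Week 6, 16 and 28 safety and endpoint assessments, and AE collection to Week 28, should continue after study drug ends or a laboratory criterion is met. The exceptions are withdrawal of consent, or the investigator's judgement that continued participation or a particular procedure is not in the participant's interest. State which sentence of section 8.4.4 applies to a withdrawn participant, and the status of someone whose doses were missed through a hold. Bring the Addendum's *could* and its CD4 wording into line with current section 7.2.

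All clinical thresholds, stopping rules and holding rules stay with the sponsor. The analysis sets need no change, since the mITT and safety sets already include everyone dosed (section 9.3). The cost is wording, plus a few follow-up visits for participants who would otherwise have left, all of them already in the schedule.

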7.3 LOST TO FOLLOW-UP

A participant will be considered lost to follow-up if he or she fails to return for 2 scheduled visits and is unable to be contacted by the study site staff.

The following actions must be taken if a participant fails to return to the clinic for a required study visit:

• The site will attempt to contact the participant and reschedule the missed visit within 2 days for any visit through week 4 and within 1 visit for weeks 6, 16 and 28 visits, and counsel the participant on the importance of maintaining the assigned visit schedule and ascertain if the participant wishes to and/or should continue in the study.

- Before a participant is deemed lost to follow-up, the investigator or designee will make every effort to regain contact with the participant (where possible, 3 telephone calls and, if necessary, a certified letter to the participant's last known mailing address). These contact attempts will be documented in the participant's medical record or study file.
- Should the participant continue to be unreachable, he or she will be considered to have withdrawn from the study with a primary reason of lost to follow-up.

8 STUDY ASSESSMENTS AND PROCEDURES

8.1 STUDY VISITS

Study visits, including screening, will occur at the IHV Clinical Research Unit at UMB. Drug doses may be infused +/-4 days to be considered in the study window (Day 0 to Week 4). Residents of DC may be provided transportation via Metro, train, or taxi, as needed.

All subjects will have a History and Physical during the screening process as part of final determination of protocol eligibility. Physical exams will be performed with study point visits at screening, Day 0, Week 6, Week 16 and Week 28. Directed physical exam will be done as needed at other study points. Subjects will be asked about their state of health and use of any concomitant medication since the previous study visit. They will also be questioned about adverse events and their adherence with study restrictions.

8.1.1.1 SCREENING

Each subject will provide informed consent of his/her free will prior to commencement of any study procedures according to ICH and Code of Federal Regulations (CFR). Each subject will be provided a copy of the signed informed consent form.

After a participant has provided informed consent, the Investigator and other study personnel will determine if they are eligible for participation in the study. Screening may begin up to 8 weeks prior to dosing with at least 14 days before Day 0.

Screening will include a review of the inclusion/exclusion criteria and completion of all screening procedures. Screening tests within the last 8 weeks prior to screening visit that have been done as part of routine medical care or at an outside facility can be used if within the acceptable time frame. Screening procedures do not need to be repeated within the 8-week screening window unless clinically indicated. Once the screening window has elapsed, subjects may be rescreened at the discretion of the PI.

At the screening visit, participants will have an H&P (including vital signs), height, weight and BMI assessment, and a medication reconciliation. Laboratory tests including CMP, CBC, HIV VL, CD4, PT/INR, hemoglobin A1c, Hepatitis B panel, Hepatitis C antibody and reflex RNA, and Troponin I and T will be collected. ECG will be done to assess for abnormalities. Females of child-bearing potential will have a serum hCG tested. Immunology labs looking at CD4 and CD8 by flow, sCD14, and inflammatory cytokines will also be done. If a subject is fasting, the procedures in section 8.1.1.3 including transient elastography may be done at this visit instead of at the "Fasting Lab Visit".

8.1.1.2 FDG-PET/CT VISIT

Twelve subjects will undergo FD -PET/CT to assess aortic inflammation at NIH. These participants will have an LDL>125. Subjects will have an FDG-PET/CT after screening, but prior to Day 0 and at week 28. Subjects will be provided transportation to and from the NIH if needed.

8.1.1.3 FASTING LAB VISIT, IF NEEDED

If subjects were not fasting at screening, they may return for fasting serum lipid and leptin levels along with transient elastography to assess for hepatic steatosis and fibrosis.

8.1.1.4 DAY 0 (FIRST INFUSION)

The participant will be started on CD24Fc or placebo on Day 0. For the first 6 subjects, prior to drug infusion and 2 hours after, blood samples for PK will be obtained. A window of +/- 10 minutes will be given around each post-infusion draw time point. Blood samples for anti-drug antibody will also be drawn before drug dosing for all subjects. For all subjects, an H&P will be performed, as well as a medication reconciliation prior to infusion. ECG should be done prior to infusion and two hours post infusion (+/- 10 minutes). Laboratory tests prior to drug infusion include: a CMP, CBC with diff, urinalysis, HIV VL, PT/INR, CD4, lipid panel, and point of care urine hCG (for females of child-bearing potential), Hs-CRP, along with research immunology and inflammation labs. Subjects participating in the FDG-PET/CT will also have GlycA, CEC, and NMR lipoprotein collected. All subjects must be fasting prior to blood draw. Adverse events will be documented.

